- Final Cohort: 6 participants will be randomized at a ratio of 5:1 to receive linaclotide at the highest dose tested/determined to be safe or matching placebo for 4-week Study Intervention Period (ie, 18, 36, 72 μg depending on the recommendation of the DSMB).

Figure 4-1 Assignment of Participants to Dose Cohorts

Sponsor decision on how to proceed with the study is based on DSMB feedback following review of all available safety data prior to each subsequent cohort.

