After at least 6 participants in each of the serial Cohorts 1 to 3 complete at least 2 weeks of double-blind study intervention, an independent DSMB will review unblinded interim safety

data. Based on this review, the DSMB will recommend whether the subsequent planned dose level should be tested. New participants will be recruited for each cohort.

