8.2. Safety Assessments

Participants must be evaluated by a physician or an appropriately trained health care professional at every visit and the evaluation must be documented. The procedures discussed below will be completed at the designated visits. Safety assessments should not be administered to the participant unless the participant is accompanied by his or her consented caregiver.

The safety assessments will include monitoring of adverse events (AEs), clinical laboratory assessments (clinical chemistry, complete blood count [CBC], urinalysis), vital sign measurements (including postural vital signs), electrocardiograms (ECGs), physical examinations, height, and weight. Evidence of severe diarrhea, especially when accompanied by dehydration, volume depletion and/or significant electrolyte or ECG abnormalities will be actively monitored throughout.

All AEs will be monitored until symptom resolution or until the condition stabilizes. A DMSB will oversee AEs and safety of the overall study (Section 10.1.6.3).

Planned timepoints for all safety assessments are provided in the SoA.

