8.2.3. Electrocardiograms

A standard 12-lead ECG will be performed at Screening (Visit 1) and at the Week 4/EOT Visit. ECGs will be performed and electronically transmitted to a central ECG laboratory for analysis according to the instructions provided by the central ECG laboratory. Measurements (in msec) will be recorded for the following parameters: heart rate, RR interval, PR interval, QRS duration, and uncorrected QT interval. QTcB (Bazett-corrected QT interval) and QTcF (Fridericia-corrected QT interval) will be calculated.

Participants with clinically significant ECG abnormalities considered to be secondary to diarrhea (ie, an AESI) must be reported to the sponsor within 24 hours, on an SAE form if considered to be serious. Non-serious events do not require submission on an SAE form; rather, these events only need to be entered into the eCRF (Section 10.3). If the AE is assessed as causally related to the use of study intervention, the participant should be discontinued from the study; however, the study physician and investigator may discuss individual participants and AEs to make this determination (Section 10.3).

The overall interpretation and determination of the clinical relevance of ECG findings using the central ECG interpretation report will be recorded in the participant's eCRF.

Sites shall transmit all study-required ECGs obtained to the ECG vendor. All ECGs performed during a given visit should be recorded on the repeating eCRF in the respective visit. Unscheduled ECGs are recorded for unscheduled visits only. All readable ECGs received by the vendor shall be sent for cardiologist over-read. The sponsor will receive all ECG data, including cardiologist assessments and ECGs that could not be evaluated.

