8.3.1. Adverse Events of Special Interest (AESIs)

AESIs are defined as significant volume depletion and/or significant electrolyte abnormalities and/or ECG abnormalities that are considered by the investigator or sponsor to be related to diarrhea. The investigator should contact the sponsor if there is any question whether the criterion for an AESIs has been met. All AESIs must be reported to the sponsor as described in Section 10.3.

8.3.2. Time Period and Frequency for Collecting Adverse Events, Serious Adverse Events, and Adverse Events of Special Interest Information

At each visit, participants are to be queried regarding any AEs or SAEs that have occurred since the previous visit. Participants will be asked to volunteer information with a nonleading question such as, "How do you feel since your last visit?" Study site personnel will record all pertinent information in the participant's eCRF. All SAE from the signing of the ICF until 30 days after the last dose of study intervention will be collected at the timepoints specified in the SoA (Section 1.3), and as observed or reported spontaneously by study participants.

All AEs from the signing of the ICF until 30 days after the last dose of study intervention will be collected at the timepoints specified in the SoA (Section 1.3), and as observed or reported spontaneously by study participants.

Medical occurrences that begin before the start of study intervention, but after obtaining informed consent will be recorded in the AE section of the eCRF.

All SAEs and serious AESIs of special interest will be recorded and reported to the sponsor or designee within 24 hours on an SAE form, as indicated in Section 10.3. Non-serious AESIs do not require submission on an SAE form; rather, these events only need to be entered into the eCRF. The investigator will submit any updated SAE data to the sponsor within 24 hours of it being available.

Investigators are not obligated to actively seek AE or SAE information after conclusion of the study participation. However, if the investigator learns of any SAE including a death, at any time after a participant has been discharged from the study, and he/she considers the event to be reasonably related to the study intervention or study participation, the investigator must promptly notify the sponsor.

The method of recording, evaluating, and assessing causality of AEs and SAEs and the procedures for completing and transmitting SAE reports are provided in Section 10.3.

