10.8.4. Week 2 (Visit 4)

During Week 2 (Visit 4), the following procedures will be performed:

- Obtain vital signs (weight, temperature (oral, rectal, or tympanic), and respiratory rate) and postural vital signs (supine systolic and diastolic BP and pulse rate) (Section 8.2.2)
- Review any AEs occurring since the last visit
- Review concomitant medications
- Review use of protocol-permitted rescue medication dispensed in IWRS where applicable.
 Participants may choose a different protocol-permitted rescue medication at any visit, where available. Additional protocol-permitted rescue medications may be dispensed as needed at any visit
- Review study intervention and rescue medication compliance and accountability
- Review eDiary completion
- Remind participant and caregiver to bring the bottle(s) of the study intervention and rescue medication to the next visit
- Remind caregivers to have the participant fast for at least 2 hours before receiving their last dose of study intervention at the study site during the Week 4 (Visit 5) Visit.

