10.8.5. Week 4/EOT (Visit 5)

Participants will arrive in a fasted state for this visit after completing at least 28 days of study intervention to receive their last dose of study intervention before or after PK sample. All randomized participants who prematurely discontinue from the study, regardless of cause, are required to be seen for the assessments completed at EOT (Visit 5, Week 4), except for PK sample collection. This visit should be scheduled at approximately the same time as when participants take their daily dose. During Week 4 (Visit 5), the following procedures will be performed:

- IWRS verification
- Perform a physical examination, including general appearance, skin, HEENT (head, ears, eyes, nose, and throat), neck, thorax/lungs, cardiovascular, abdomen, musculoskeletal, lymph

nodes, neurologic (including mental status), and visual inspection of the lumbosacral and perianal region.

- Complete modified Rome III assessment
- Obtain vital signs (weight, temperature (oral, rectal, or tympanic), and respiratory rate) and postural vital signs (supine systolic and diastolic BP, and pulse rate) (Section 8.2.2)
- Obtain standard 12-lead ECG (supine)
- Obtain clinical laboratory tests consisting of clinical chemistry, hematology and urinalysis. All laboratory tests requiring blood draws should be collected at the same time
- Review any AEs occurring since the last visit
- Review concomitant medications
- PK sample will be obtained in participants who will be completing the study intervention at this visit.
- Pre-dose or post-dose PK sampling should be obtained at the same time as clinical lab tests described above to avoid an extra needle stick.
- Pre-dose sample will be obtained from participants assigned to this group at the clinic before the administration of the last dose of study intervention. Post-dose PK sample will be obtained 1-8 hours after the last dose of study intervention in participants assigned to the post-dose PK group. The last dose of study intervention should be administered after confirming the participant has fasted for at least 2 hours. Participants may resume eating 30 minutes after receiving their last dose of study intervention at the study site.
- Obtain date and time of the dose of study intervention prior to PK sample collection
- Obtain standard 12-lead ECG (supine)
- Review use of protocol-permitted rescue medication dispensed in IWRS where applicable.

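### The DSMB can recommend the next dose, double the last, or the final-cohort dose before any reviewed child has a scheduled on-treatment electrolyte or ECG value, and no text requires it to see those values before dosing starts

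*Protocol*

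**What the plan says.** Review timing. Protocol 4.3 sets the review of unblinded safety data thus: "After at least 6 participants in each of the serial Cohorts 1 to 3 complete at least 2 weeks of double-blind study intervention". Protocol 4.1 and SAP 4.0 and 13.1 give the same minimum. The DSMB then recommends whether the next planned dose should be tested. Under 4.1, the sponsor's decision "is based on DSMB feedback following review of all available safety data prior to each subsequent cohort". No minimum content is set for those data. In the last step, "6 participants will be randomized at a ratio of 5:1 to receive linaclotide at the highest dose tested/determined to be safe".

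Measurement timing. Protocol 8.2.3: "A standard 12-lead ECG will be performed at Screening (Visit 1) and at the Week 4/EOT Visit". Laboratory tests follow the same pattern in the Schedule of Activities (protocol 1.3, SAP Table 4-1): Screening and Visit 5. For Visit 5, protocol 10.8.5 lists: "Obtain clinical laboratory tests consisting of clinical chemistry, hematology and urinalysis". Protocol 10.8.4 opens with "During Week 2 (Visit 4), the following procedures will be performed"; its list covers vital signs with weight and postural signs, adverse events, medications, compliance and eDiary, but no blood draw and no ECG.

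What counts as the special risk. Protocol 8.3.1: "AESIs are defined as significant volume depletion and/or significant electrolyte abnormalities and/or ECG abnormalities", where these are judged related to diarrhea. Protocol 8.2 adds: "Evidence of severe diarrhea, especially when accompanied by dehydration, volume depletion and/or significant electrolyte or ECG abnormalities will be actively monitored throughout".

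**The concern.** The review is tied to the 2-week mark, but two of the three parts of the event of special interest are first measured on schedule at Week 4. At the minimum, a recommendation to escalate can therefore be made with no scheduled on-treatment electrolyte or ECG value from children still taking the drug.

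The decision carries weight. Protocol 4.2 explains that the ascending design was chosen because linaclotide is contraindicated under 6 years and clinical data at this age are lacking. Protocol 2.2.4 reports severe diarrhea in adults with hypokalemia and hyponatremia, some of it needing hospital care or intravenous fluids. Each planned step doubles the dose. Most children planned for linaclotide start after one of these reviews, and the final cohort's dose depends on a judgment of which dose is safe.

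**Working it through.** **1. Planned numbers.** The plan's total reproduces: 3 × 8 + 6 = 30. At 3:1 and 5:1 allocation, linaclotide has 6 + 6 + 6 + 5 = 23 and placebo 2 + 2 + 2 + 1 = 7. Children planned for linaclotide who start after a review: 6 + 6 + 5 = 17 of 23. Dose steps: 36/18 = 2 and 72/36 = 2. The sample size has no power calculation to check.

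**2. Gap between review and measurement.** Two completed weeks is Day 15; Week 4 is Day 29 (+2). The sixth child's first scheduled on-treatment chemistry and ECG therefore come 29 − 15 = 14 days after the earliest review, or 16 with the window.

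**3. How many of the 6 are measured at the earliest review.** Only children who have reached Day 29 count. If randomizations are evenly spaced (an assumption), the count is 0 of 6 at 0 to 2 days apart, 1 at 3 days, 3 at 5 days, 4 at 7 days and 5 at 14 days.

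Now let enrollment be random (Poisson) at r children per week within a cohort, with the data cut w weeks short of the sixth child's Day 29. With no review lag, w = 2. The child k places before the sixth has reached Day 29 with probability P_k = P(Poisson(r × w) ≤ k − 1), for k = 1 to 5. The mean number measured is the sum of the P_k, and the chance that none is measured is 1 − P_5. On average 6/8 = 0.75 of those measured are on linaclotide, taking exactly 6 and 2 per cohort.

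| r (assumed) | P_1 + … + P_5, no lag | Mean of 6 | On linaclotide | None measured |
|---|---|---|---|---|
| 0.5 | 0.368 + 0.736 + 0.920 + 0.981 + 0.996 | 4.0 | 3.0 | 0.4% |
| 1 | 0.135 + 0.406 + 0.677 + 0.857 + 0.947 | 3.0 | 2.3 | 5% |
| 2 | 0.018 + 0.092 + 0.238 + 0.433 + 0.629 | 1.4 | 1.1 | 37% |
| 4 | 0.000 + 0.003 + 0.014 + 0.042 + 0.100 | 0.2 | 0.1 | 90% |

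**4. Effect of review lag.** A 7-day lag makes w = 1, so r × w halves. At 1, 2 and 4 per week the mean becomes 4.0, 3.0 and 1.4 of 6, and the chance of none 0.4%, 5% and 37%. After a 14-day lag all 6 have reached Day 29, apart from the +2 window.

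**5. Does Week 4 fall before the next dose?** Screening lasts at least 14 days and preintervention at least 14, so the lead-in is at least 28 days (protocol 1.3; 10.8.1 gives 4 to 7 weeks). If next-cohort screening starts after the review, the sixth child's Week 4 tests are collected at least 28 − 16 = 12 days before a new child takes a first dose. Read time must fit in that margin.

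**The case against.** The strongest reply is that the children are better protected than the review trigger suggests, and much of it stands.

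- A reader might infer that the next cohort will be dosed before Week 4 values exist. The documents do not support that. Protocol 4.1 counts screening within each cohort and places the review before each later one, so the 28-day lead-in will usually cover the 14 to 16 days. The sponsor may also interrupt the study on new safety data (7.1.2), and the DSMB may meet ad hoc (10.1.6.3).
- A reader might take protocol 8.2 as a promise of electrolyte and ECG testing throughout treatment. Its subject is severe diarrhea, especially with such abnormalities, and the same section refers to the schedule for timepoints.
- Symptomatic cases have other routes to notice: adverse event review, weight and postural vital signs at Week 2, caregiver training on dehydration (10.8.2) and discretionary tests (10.2). Children who stop early are to have EOT chemistry and ECG (7.1.1, 10.8.5).
- The 2-week mark is a floor. Slow enrollment or a later meeting fills the gap. LIN-MD-63, in another pediatric population, closed at 101 of about 260 children for slow enrollment (2.2.2), which makes the low-rate rows more plausible.
- A reader might turn the gap into a detection probability, for instance from the absence of such events among the 214 linaclotide-treated children in LIN-MD-62 and LIN-MD-63. Those events were diarrhea-related and judged so by the investigator or sponsor. What scheduled tests alone would add is a clinically silent abnormality, and the documents give no rate for that. I therefore give no detection figure.

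What survives is that neither the protocol nor the SAP makes the DSMB look at the Week 4 values before the next dose is given. The Charter might, but it is not provided.

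**Conclusion.** The point holds as a gap in what the escalation decision must rest on. The recommendation on the next dose, or on the final-cohort dose, can be made with as few as 0 of 6 children having a scheduled on-treatment electrolyte or ECG value. That minimum follows from the schedule alone. The typical number does not: the means of 4.0 to 0.2 of 6 rest on assumed enrollment of 0.5 to 4 children per week and on no lag between the sixth child's Day 15 and the data cut, and any lag raises them.

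The volume-depletion part of the event definition is covered at Week 2, so the gap concerns electrolytes and ECG in children still on drug with no triggered test. The documents do not show that children would be dosed before Week 4 values exist. They show only that no one is required to put those values before the DSMB first. This is a modest weakness that is cheap to close.

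**What to change.** In protocol 4.1 and 4.3 and SAP 4.0 and 13.1, keep the 2-week review as permission to start screening for the next cohort. Then add that no child in the next or final cohort is dosed until the DSMB has received the Week 4 chemistry and ECG from the children on whom the review was based, and has confirmed its recommendation. For children who stopped early, use the EOT results and show days on drug. Report missing or failed tests to the DSMB without letting them block its decision.

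Cost: one short data update to the DSMB per cohort, with no new visit, blood draw or ECG. There is usually no delay, because Week 4 falls 14 to 16 days after the 2-week mark and inside the lead-in of 28 days or more. If next-cohort screening has already run, the delay is at most about 2 weeks plus laboratory and ECG read time.

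I would not add chemistry and ECG at Visit 4. That means an extra needle stick in children aged 2 to 5, which 10.8.5 tries to avoid, under a 12 mL blood limit whose remaining room cannot be checked from the documents.

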4.4. End of Study Definition

The end of the study is defined as the date of the last visit of the last participant in the study or last scheduled procedure shown in the SoA for the last participant in the study globally.

A participant is considered to have completed the study if he/she has completed all visits of the study including the last visit.

4.5. End of Cohort Definition

The end of the cohort is defined as the date of the last visit of the last participant in the cohort or last scheduled procedure shown in the SoA for the last participant in the cohort globally.

5. Study Population

Prospective approval of protocol deviations to recruitment and enrollment criteria, also known as protocol waivers or exemptions, is not permitted.

Where applicable for this pediatric population, the term "participant" refers to the participant, parent, and/or caregiver.

5.1. Inclusion Criteria

The targeted participant population will include male and female participants, 2 to 5 years of age. Participants are eligible to be included in the study only if all of the following criteria apply:

1.	Age and Weight
1.01	Male and female participants must be ages 2 to 5 years, (inclusive) at the time the parent/guardian/LAR has provided signed consent
1.02	Participant weighs $\geq 10~kg$ at the time the parent/guardian/LAR has provided signed consent
2.	Type of Participant and Disease Characteristics

2.01	Participant meets modified Rome III criteria for FC: For at least 2 months before Screening (Visit 1) (for participants aged ≥ 4 years old), or for at least 1 month before Screening (Visit 1) (for participants aged < 4 years old), the participant has had 2 or fewer defecations (with each defecation occurring in the absence of any laxative, suppository, or enema use during the preceding 24 hours) per week.		
	In addition, at least once per week, participant must meet 1 or more of the following:		
	a. History of retentive posturing or excessive volitional stool retention		
	b. History of painful or hard bowel movements (BMs)		
	c. Presence of a large fecal mass in the rectum		
	d. History of large diameter stools that may obstruct the toilet		
	e. At least one episode of fecal incontinence per week after the acquisition of toileting skills		
2.02	Participant is willing to discontinue any laxatives used before the Preintervention Visit in favor of the protocol- permitted rescue medicine.		
2.03	Participant has an average of fewer than 3 SBMs per week during the 14 days before the randomization day and up to the randomization (including the clinic eDiary assessments reported before administration of first dose of double-blind study intervention on the randomization day). An SBM is defined as a BM that occurs in the absence of laxative, enema, or suppository use on the calendar day of the BM or the calendar day before the BM		
2.04	Caregiver is compliant with eDiary requirements by completing daily assessments for 10 out of the 14 days immediately preceding the Randomization Visit.		
3.	Informed Consent		
3.01	Parent/guardian/LAR and caregiver must provide written informed consent before the initiation of any study-specific procedures		
3.02	Caregiver who will be completing the eDiary is able to read and/or understand the assessments in the eDiary device and must undergo training		

CONFIDENTIAL

linaclotide

5.2. Exclusion Criteria

CONFIDENTIAL

linaclotide

Participants are excluded from the study if any of the following criteria apply:

1.	Medical Conditions
1.01	Participant has clinically significant findings on a physical examination, vital sign assessment, ECG, or clinical laboratory tests at Screening (Visit 1), as determined by the investigator, based on consideration of whether the finding could represent a safety concern or a condition that would be exclusionary, could prevent the participant from performing any protocol assessments, or could confound study assessments.
1.02	Caregiver reports the participant had more than 1 loose, mushy stool (eDiary-recorded stool consistency of 6 on the Bristol Stool Form Scale [BSFS]) or any watery stool (eDiary-recorded stool consistency of 7 on the BSFS) with any SBM that occurred in the absence of laxative use on the calendar day of the BM or the calendar day before the BM during the 14 days before the randomization day and up to the randomization (including the daily eDiary assessment reported before administration of first dose of double-blind study intervention on the randomization day)
1.03	For participants aged ≥ 4 years old: Participant meets Rome III criteria for Child/Adolescent IBS: At least once per week for at least 2 months before Screening (Visit 1), the participant has experienced abdominal discomfort (an uncomfortable sensation not described as pain) or pain associated with 2 or more of the following at least 25% of the time: a. Improvement with defecation b. Onset associated with a change in frequency of stool c. Onset associated with a change in form (appearance) of stool
1.04	Participant has (a) fecal impaction at Visit 2 after failing outpatient clean-out during the Screening Period or (b) fecal impaction at Visit 3.
1.05	Participant has required manual dis-impaction any time prior to randomization or dis- impaction during in-patient hospitalization (for impaction) within 1 year prior to randomization
1.06	Participant currently has both unexplained and clinically significant alarm symptoms (lower GI bleeding [rectal bleeding or heme-positive stool], iron-deficiency anemia, or any unexplained anemia, or weight loss) and systemic signs of infection or colitis, or any neoplastic process

1.07	Partici	pant has had surgery that meets any of the following criteria:	
	a. Surgery to remove a segment of the GI tract at any time before Screening (Visit 1)		
	b. Surgery of the abdomen, pelvis, or retroperitoneal structures during the 6 months before the Screening Visit		
	c. An appendectomy or cholecystectomy during the 60 days before Screening (Visit 1)		
	d. Other major surgery during the 30 days before Screening (Visit 1)		
1.08	Participant has an acute or chronic condition that, in the investigator's opinion, would limit the participant's ability to complete or participate in this clinical study		
1.09	Participant has a known or suspected mechanical bowel obstruction or pseudo-obstruction.		
1.10	Participant has a known allergy or sensitivity to the study intervention or its components or other medications in the same drug class		
1.11	Participant has any of the following conditions:		
	a.	Celiac disease, or positive serological test for celiac disease or the condition is suspected but has not been ruled out by endoscopic biopsy	
	b.	Cystic fibrosis	
	c.	Hypothyroidism that is untreated or treated with thyroid hormone at a dose that has not been stable for at least 3 months prior to Screening (Visit 1)	
	d.	Down's syndrome or any other chromosomal disorder	
	e.	Active anal fissure (ie, participant reports having streaks of blood on the stool or on toilet paper and/or pain/crying with bowel movement within 2 weeks prior to Screening). (Note: Anal fissures that have resolved at least 2 weeks prior to screening would not be exclusionary.) However, if in the investigator's opinion, an anal fissure(s) may be the primary cause of participant's modified Rome III FC criteria, the participant would not be eligible to participate in the study.	
	f.	Anatomic malformations (eg, imperforate anus, anal stenosis, anterior displaced anus)	
	g.	Intestinal nerve or muscle disorders (eg, Hirschprung disease, visceral myopathies, visceral neuropathies)	
	h.	Neuropathic conditions (eg, spinal cord abnormalities, neurofibromatosis, tethered cord, spinal cord trauma)	
	i.	Lead toxicity, hypercalcemia	
	j.	Neurodevelopmental disabilities (early-onset, chronic disorders that share the essential feature of a predominant disturbance in the acquisition of cognitive,	

	motor, language, or social skills, which has a significant and continuing impact on the developmental progress of an individual) producing a cognitive delay that precludes comprehension and completion of the daily eDiary or other study-related questionnaires (Note: Participants are excluded if the person who will be completing the daily eDiary or other study-related questionnaires meets this criterion.)	
	k. Inflammatory bowel disease	
	Childhood functional abdominal pain syndrome	
	m. Childhood functional abdominal pain	
	n. Poorly treated or poorly controlled psychiatric disorders that might influence his or her ability to participate in the study	
	o. Lactose intolerance that is associated with symptoms which could confound the assessments in this study	
	p. History of cancer other than treated basal cell carcinoma of the skin. (Note: Participants with a history of cancer are allowed provided that the malignancy has been in a complete remission before the Randomization Visit. A complete remission is defined as the disappearance of all signs of cancer in response to treatment.)	
2.	Prior/Concomitant Therapy	
2.01	Participant used a protocol-specified prohibited medicine before the start of the Preintervention Period or failed to meet the stable-dose requirements of certain medications	
2.02	Participant used rescue medication on the calendar day before the Randomization Visit and on the day of the Randomization Visit until randomized	
2.03	Breastfeeding is allowed unless the mother is taking protocol-specified prohibited medicines (Section 6.5.1)	
	Prior/Concurrent Clinical Study Experience	
3.	Prior/Concurrent Clinical Study Experience	
3. 3.01	Prior/Concurrent Clinical Study Experience Participant received a study intervention during the 30 days before Screening (Visit 1) or is planning to receive study intervention (other than that administered during this study)	
	Participant received a study intervention during the 30 days before Screening (Visit 1) or	

4.02	Participant's parent/guardian/LAR or caregiver has been directly or indirectly involved in the conduct and administration of this study as an investigator, study coordinator, or other study staff member. In addition, any participant, parent/guardian/LAR or caregiver who has a first-degree family member, significant other, or relative residing with him/her directly or indirectly who is involved in this study
4.03	For participants $aged \ge 4$ years old: Participant has a history of non-retentive fecal incontinence

Rationale for Inclusion and Exclusion Criteria

The inclusion and exclusion criteria are meant to identify a population of pediatric participants that is well characterized as having FC who fulfill modified Rome III criteria for childhood FC.

